6 TREATMENT PLAN

6.1 Baseline Tests and Procedures

Patients who are eligible and enrolled in the study but do not immediately initiate study treatment are expected to meet eligibility criteria until the time when treatment is initiated. For example, if an enrolled patient's post-enrollment (pre-treatment) liver function tests no longer meet eligibility criteria, treatment should be held until the investigator can provide guidance to the study team.

6.2 Administration of Study Treatment

- 6.2.1 AR-42 Administration and Treatment Schedule
 - AR-42 tablets will be taken orally once per day on 3 non-consecutive days per week (eg, Monday, Wednesday, and Friday) during the first 3 weeks of each 4-week cycle (ie, a total of 9 doses). A 7-day "AR-42 rest period" during which AR-42 will not be taken is required at the end of each cycle (ie, AR-42 will not be taken by the patient during week 4 of each 4-week cycle).
 - If treatment must be interrupted during the cycle, the cycle may be extended to a maximum of 5 weeks. If the cycle has been extended to 5 weeks, all doses of AR-42 (ie, a total of 9 doses) must be taken during the first 4 weeks of the extended cycle (ie, if the cycle was extended, AR-42 will not be taken by the patient during week 5 of the 5-week cycle).
 - Patients will be instructed as follows:
 - Take AR-42 once per day on 3 non-consecutive days during the first 3 weeks of each 4-week cycle.
 - Take AR-42 tablets with water on an empty stomach, ideally the first thing in the morning at least 1 hour before breakfast. If necessary, doses can be taken at least 1 hour before or at least 2 hours following any meal.
 - Swallow the AR-42 tablets whole.
- 6.2.2 Pazopanib Administration and Treatment Schedule
 - Pazopanib tablets will be taken orally once daily continuously during each treatment cycle. There are no scheduled breaks in pazopanib therapy.
 - Patients will be instructed as follows:
 - Take pazopanib once daily during each 4-week cycle
 - Take pazopanib tablets with water on an empty stomach, ideally the first thing in the morning at least 1 hour before breakfast. If necessary, doses can be taken at least 1 hour before or at least 2 hours following any meal.
 - Swallow the pazopanib tablets whole.

6.3 Missed Doses

6.3.1 AR-42 Missed Doses

If an AR-42 dose is missed, the missed dose of AR-42 should be taken on the same day, as soon as the patient remembers. If the missed dose cannot be taken on the scheduled day, the patient should take the dose on the next day and adjust the schedule by one day (eg, from Monday, Wednesday, and Friday to Tuesday, Thursday, and Saturday) for the remainder of that cycle. The usual schedule should be resumed at the beginning of the next cycle as long as there has been a 7-day rest period.

6.3.2 Pazopanib Missed Doses

If a pazopanib dose of pazopanib is missed, the missed dose of pazopanib should be taken on the same day, as soon as the patient remembers. Two doses of pazopanib should not be taken on the same day to make up for doses that were missed on the previous day.

6.4 Monitoring Patient Compliance

Patients will be instructed to record the AR-42 and pazopanib doses they have taken on the study medication diary that will be provided. Also, patients will be instructed to bring their diary and any unused supply of AR-42 and pazopanib to each visit with their study team.

Patient reports of self-administration, review of the study medication diary, and pill counts will be used to assess the patient's compliance with the oral study treatment regimen.

6.5 Duration of Therapy

Treatment will continue until any of the following occurs (also see information regarding study withdrawal in Section 5.2):

- Interruption in either of the study medications due to unresolved toxicity for a period of more than 21 consecutive days
- AE that requires discontinuation of **both** study medications (see Section 7)
- Disease progression
- Patient decision to discontinue study treatment
- Investigator determination that discontinuation is in the patient's best medical interest
- Withdrawal of study sponsor support

6.6 AR-42 and Pazopanib Dose-Escalation Plan

The dose-escalation plan is based on the available dose levels listed on Table 1, the dose level instructions outlined on Table 2, and the modified 3+3 design on Table 3.

- The initial cohort of patients will be assigned to an AR-42 dose of 20 mg taken once per day on 3 non-consecutive days during the first 3 weeks of each 4-week cycle and a pazopanib dose of 600 mg once daily continuously.
- The treatment schedule as described in Section 6.2 will remain the same for all dose levels.
- The initial escalation will only affect the pazopanib dose so that the FDA-approved full dose of pazopanib (800 mg) is provided early in the dose-escalation plan. In subsequent dose-escalation steps, the dose of AR-42 will be increased in 10-mg increments until the maximum AR-42 dose of 40 mg is reached.
- If the number of DLTs indicates that the MTD has been exceeded with a pazopanib dose of 800 mg, the pazopanib dose will be decreased to 600 mg and the AR-42 dose will continue to increase in 10-mg increments regardless of relationship of the DLT to one or both study medications.

-		600 mg	800 mg
	10 mg	-1	N/A
AR-42 Dose	20 mg	1 (Starting Dose Level)	2
Dose	30 mg	3B	3A
	40 mg	4B	4A

Table 1. AR-42 and Pazopanib Dose Levels

Pazopanib Dose

	AR-42 Dose (Taken orally)	Pazopanib Dose (Taken orally)	
Dose Level	Once per day on 3 non-consecutive days/week during the first 3 weeks of each 4-week cycle	Once per day continuously during each 4-week cycle	
-1	10 mg	600 mg	
 If 0 or 1 DLT is observed with Dose Level -1, the MTD will be Dose Level -1. If ≥ 2 DLTs are observed at Dose Level -1, the lowest possible dose level was not tolerated. 			
1 (Starting Dose Level)	20 mg	600 mg	
 If 0 or 1 DLT is observed with Dose Level 1, the next cohort will receive Dose Level 2. If ≥ 2 DLTs are observed at Dose Level 1, the next cohort will receive Dose Level -1. 			
2	20 mg	800 mg	
 If 0 or 1 DLT is observed with Dose Level 2, the next cohort will receive Dose Level 3A. If ≥ 2 DLTs are observed at Dose Level 2, the next cohort will receive Dose Level 3B. 			
3A	30 mg	800 mg	
3B	30 mg	600 mg	
 If 0 or 1 DLT is observed with Dose Level 3A, the next cohort will receive Dose Level 4A. If ≥ 2 DLTs are observed at Dose Level 3A, the next cohort will receive Dose Level 3B. If 0 or 1 DLT is observed with Dose Level 3B, the next cohort will receive Dose Level 4B. If ≥ 2 DLTs are observed at Dose Level 3B, the highest dose level without ≥ 2 DLTs will be the MTD. 			
4A	40 mg	800 mg	
4B	40 mg	600 mg	
 If 0 or 1 DL 	T is observed with Dose Level 4/	A, the MTD will be Dose Level 4A.	
– If ≥ 2 DLTs	are observed at Dose Level 4A,	the next cohort will receive Dose Level 4B.	
 If 0 or 1 DLT is observed with Dose Level 4B, the MTD will be Dose Level 4B. If ≥ 2 DLTs are observed at Dose Level 4B, the MTD will be the highest dose level without ≥ 2 DLTs. 			

Table 2. AR-42 and Pazopanib Dose-Escalation Guidelines

6.7 Definitions of Dose-Limiting Toxicity, Maximum Tolerated Dose, and Recommended Phase 2 Dose

6.7.1 DLT-Evaluable Criteria

The DLT evaluation period will be the first treatment cycle. Patients must have taken a minimum of 6 AR-42 doses **and** a minimum of 21 pazopanib doses during cycle 1 to be considered evaluable for DLT, if DLT has not been observed at the delivered dose.

6.7.2 DLT Definition

DLT is defined as **any** ≥ **grade 3** toxicity occurring during the DLT evaluation period and attributed to one or both of the study medications **EXCEPT the following:**

- The first incidence of grade 3 PPE at any dose level (subsequent incidences of grade 3 PPE will be considered DLT)
- Grade 3 nausea and vomiting in the absence of adequate prophylaxis and/or responsive to medical management within 48 hours
- Grade 3 diarrhea in the absence of adequate prophylaxis and/or responsive to medical management within 48 hours
- Grade 3 fatigue responsive to medical management
- Grade 3 asymptomatic hypertension lasting \leq 7 days
- Grade 3 electrolyte abnormalities that are corrected within 48 hours and, when corrected, can be maintained
- Grade 3 asymptomatic lipase elevation lasting \leq 7 days
- Grade 3 decrease in platelet count if no clinically significant hemorrhage has occurred
- Grades 3 and 4 decrease in white blood cell count
- Grade 3 decrease in neutrophil count
- Grade 4 decrease in neutrophil count lasting ≤ 7 days
- Grades 3 and 4 decrease in lymphocyte count

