6.7.4 RP2D

The RP2D may be equal to, but may not exceed, the MTD. A RP2D below the MTD may be considered given the overall tolerability of the treatment regimen including the frequency of AEs that are not DLTs and the frequency of dose modifications.

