Grade 2 toxicity that is persistent, intolerable, or unresponsive to optimal management	At the investigator's discretion, reduce AR-42 by one dose reduction step. ^B
Grade 3 toxicity	Hold/omit ^A until resolution to ≤ grade 1, baseline, or tolerable grade 2; reduce dose by one dose reduction step when resuming treatment. ^B
Grade 4 toxicity	Discontinue study treatment.
A. If recovery takes longer than the first 4 we	eks of the cycle, any remaining doses are omitted. DLT evaluation period [Section 6.7.1]), the dose may be

Table 5. AR-42 Dose Modification Instructions

B. At the investigator's discretion (after the DET evaluation period [Section 6.7.1]), the dose may be escalated to the most recent dose taken by the patient when treatment resumes.
C. Excludes alopecia, nausea and vomiting that improve with antiemetic therapy, lymphopenia, and other lab abnormalities that are asymptomatic and/or not clinically significant per investigator.

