8.5 Procedures for Recording AEs, SARs, SAEs, SSARs, DLTs, and UPs

All AEs (including SAEs, SARs, and SSARs), DLTs, and UPs will be recorded in MCC's OnCore Clinical Trials Management System. In most cases, it is acceptable to record in OnCore only the highest grade of a toxicity occurring during a particular study segment when an event has serial fluctuations in grade over time.

SAEs will be entered into the OnCore SAE domain. UPs will be entered into the OnCore Deviations domain. An SAE that is both an SAE and a UP will be entered in both domains. For all SAEs, a corresponding entry should be made in the routine AE record to match the event entries in the SAE domain.

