12 STUDY CALENDARS

The schedule of tests, exams, disease assessments, collection of samples for correlative studies, and study treatment are listed on 2 tables: requirements during screening through treatment cycle 1 on Table 19 and requirements during remaining treatment beginning with cycle 2 and continuing through study follow-up on Table 20.

Table 19. Study	y Calendar - Scree	ening Through Tre	atment Cycle 1

Tests, Exams, and Other Requirements	Screening (Days Prior to Cycle 1, Day 1)			Study Treatment – Cycle 1				
	Within 28 Days	Within 14 Days	Within 7 Days	Day 1 ^A	Day 8 ^B	Day 15 ^B	Day 22 ^B	Day 29 ^B (If cycle wa extended) ⁶
Informed Consent	Х							,
Demographics	Х							
Medical/Surgical History	Х							
Height	Х							
Weight		Х		Х	Х	Х	Х	Х
Vital Signs		Х		Х	Х	Х	Х	Х
BP		Х		Х	Х	Х	Х	Х
Performance Status		Х		Х	Х	Х	Х	Х
Baseline Conditions/Symptoms		Х						
AE Assessment					Х	Х	Х	Х
Concurrent Medications ^D		Х			Х	Х	Х	Х
Physical Exam		Х		Х	Х	Х	Х	Х
CBC with Differential		Х		Х	Х	Х	Х	Х
Platelet Count		Х		Х	Х	Х	Х	Х
Serum Chemistry ^E		Х		Х	XF	XF	XF	XF
aPTT and INR		Х						
Lipase		Х						
TSH and T4		Х						
Serum Pregnancy Test ^G			Х					
Urinalysis for protein		XH						
12-Lead ECG	Х				Х	Х	Х	Х
LVEF Assessment ^J	Хĸ							
Imaging/Disease Assessment	XL							
Correlative Tumor Sample Collection					-	Х ^м		
AR-42 PO ^N				Once daily 3 days/week during 1 st 3 weeks			Xo	
Pazopanib PO ^N						Xo		
Study Med Diary Review/Pill Count				Х	Х	Х	Х	Х

Table 19 Footnotes:

- A. Except for BP and vital signs, baseline evaluations performed within 1 week prior to initiation of study treatment do not need to be repeated on cycle 1, day 1.
- B. Within +/- 24 hours.
- C. Day 29 requirements only apply to patients who had a treatment interruption earlier in the cycle that required extending the cycle beyond 28 days (up to a maximum of 35 days).
- D. Include over-the-counter medications.
- E. Serum chemistry includes the following panels and tests: basic metabolic panel (sodium, potassium, carbonate, chloride, glucose, calcium, BUN, and creatinine); hepatic panel (ALT, AST, ALP, total bilirubin, direct bilirubin, albumin, and total protein); and magnesium and phosphorous.
- F. Refer to Table 8 for instructions regarding increased frequency of liver function monitoring (weekly for at least 4 weeks) when pazopanib-related elevations (AST, ALT, bilirubin) occur.
- G. Only required for WCBP; see Section 4.1.12 for the definition of WCBP.

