- H. If urinalysis reading for protein is ≥ 2+ (100 mg/dL), a 24-hour urine sample must be collected and tested (see Section 4.1.6 for related eligibility criterion).
- I. Refer to Section 4.2.13, Section 6.8, and Table 7 for instructions related to QTc interval prolongation.
- J. Assessment may be performed by echocardiogram or by a nuclear study (eg, MUGA scan; first-pass technique).
- K. Determination of LVEF is required within 3 months prior to cycle 1, day 1 study treatment.
- L. Baseline imaging **must be contrast-enhanced** and include the following:
 - Chest CT, CT or MRI of abdomen and pelvis, and all other suspected sites of disease **within 28 days** prior to initiation of study treatment; for patients with a CT contrast allergy, the chest CT may be performed without contrast or, if the chest is not a known site of disease, a chest x-ray may be used
 - Brain CT or MRI within 8 weeks prior to initiation of study treatment
- M. Collection of tumor samples archived following the most recent biopsy or surgery; tumor samples must be requested by the end of cycle 2 (Section 11).
- N. Refer to Sections 6.1 through 6.6 for treatment-related instructions including the AR-42 and pazopanib dose levels.
- O. If cycle has been extended to 5 weeks, AR-42 doses must be given during the 1st 4 weeks of the cycle allowing a 1-week AR-42 rest period (Section 6.2.1); pazopanib continues daily.

Tests, Exams, and Other Requirements	Cycle 2		Cycle 3	Cycle 4	End of	End of
	Day 1 ^A	Day 15 ^B	Day 1 ^A	Day 1 ^A	Treatment ^c	30-Day Follow-Up
Weight	Х		Х	Х	Х	
Vital Signs	Х		Х	Х	Х	
BP	Х	Х	Х	Х	Х	
Performance Status	Х		Х	Х	Х	
Assessment of AEs	Х		Х	Х	Х	XD
Concurrent Medications ^E	Х		Х	Х	Х	
Physical Exam	Х		Х	Х	Х	
CBC with Differential	Х	Х	Х	Х	Х	
Platelet Count	Х	Х	Х	Х	Х	
Serum Chemistry ^F	XF	XF	XF	X ^F	Х	
Lipase	Х		Х	Х	Х	
TSH and T4				X ^G (Every 3 cycles)		
Urinalysis for Protein			Х ^н (Every 2 cycles)			
12-Lead ECG ^I	х			X ^J (Every 2 cycles)		
LVEF Assessment ^K				X ^L (Every 3 cycles)		
Tumor Imaging/Disease Assessment ^M			X ^N (Every 2 cycles)		x	0
Correlative Tumor Sample Collection	х	P				
AR-42 PO ^Q	Once	daily 3 days/w				
Pazopanib PO ^Q	Once daily continuously ^R					
Study Medication Diary Review & Pill Count	Х		Х	Х	х	

72

 Table 20. Study Calendar – Treatment Beginning with Cycle 2 Through Follow-Up

Table 20 Footnotes:

- A. Within 3 days prior to or on day 1 of each treatment cycle.

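### The cycle 1 DLT rule turns on the occurrence and duration of grade 3 lipase elevation, but no on-treatment lipase is scheduled before the cycle 2 day 1 draw

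*Combined protocol and SAP*

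**What the plan says.** Section 6.7.2 defines a DLT as any attributed toxicity of grade 3 or higher in the DLT period, apart from a list of exceptions. One exception is "Grade 3 asymptomatic lipase elevation lasting" seven days or less. A symptomatic, longer or grade 4 lipase elevation therefore remains a DLT. Section 6.7.1 fixes the window: "The DLT evaluation period will be the first treatment cycle".

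Table 19 (screening and cycle 1) marks lipase once, at screening within 14 days, and not on day 1, 8, 15, 22 or 29. Serum chemistry is drawn at each of those visits, but footnote E itemises it as a basic metabolic panel plus "hepatic panel (ALT, AST, ALP, total bilirubin, direct bilirubin, albumin, and total protein); and magnesium and phosphorous", without lipase. Visits on days 8, 15, 22 and 29 have a window of "Within +/- 24 hours".

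Table 20 marks lipase on day 1 of cycles 2, 3 and 4 and at end of treatment, but not on cycle 2 day 15. Footnote A allows the day 1 tests "Within 3 days prior to or on day 1 of each treatment cycle".

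**The concern.** Applying the exception takes two facts: that an elevation occurred in cycle 1, and how long it lasted. The calendar supplies neither reliably. An asymptomatic laboratory change gives no clinical reason for an unscheduled test, and no section requires one.

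The protocol's own comparators suggest an oversight. Section 6.7.2 sets a seven-day limit on two other exceptions, grade 3 hypertension and grade 4 neutropenia. Blood pressure and the differential count are both taken weekly in cycle 1. Lipase is the only one of the three with no scheduled on-treatment measurement before the end of the cycle.

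Small numbers drive the decision. Under Table 3, 0 of 3 patients with DLT escalates, 1 of 3 expands the cohort, and 2 or more means the MTD has been exceeded. A single unseen event can change that step.

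**Working it through.** The plan gives no figure for lipase ascertainment, so there is none to reproduce. The check has four steps.

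**1. Date of the first on-treatment lipase.** In a 28-day cycle, cycle 2 day 1 is day 29. Footnote A of Table 20 allows up to 3 days earlier, so the draw falls on days 26-29. If cycle 1 runs its maximum of 35 days, cycle 2 day 1 is day 36 and the draw falls on days 33-36. The extra day 29 visit of an extended cycle has no lipase.

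**2. Share of episodes seen.** Assumptions, not taken from the documents: onset day *o* is equally likely on each of days 2-28 (27 values), and lipase is elevated from day *o* to day *o + D - 1* for a fixed duration *D*. A draw on day *d* sees the episode if *o ≤ d ≤ o + D - 1*.

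Example, *D* = 8: a draw on day 26 sees onsets 19-26, which is 8/27 = 30%. A draw on day 29 sees onsets 22-28, which is 7/27 = 26%.

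| Duration | Single draw, days 26-29 | With days 8, 15 and 22 added |
|---|---|---|
| 7 days | 6-7/27 (22-26%) | 25-27/27 (93-100%) |
| 8 days | 7-8/27 (26-30%) | 25-27/27 (93-100%) |
| 14 days | 13-14/27 (48-52%) | 25-27/27 (93-100%) |
| 21 days | 20-21/27 (74-78%) | 25-27/27 (93-100%) |

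Moving each weekly visit by -1, 0 or +1 day lowers the 8-day figure with added draws to 24-27/27 (89-100%). The 14-day and 21-day figures stay at 93-100%.

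For a 35-day cycle with onset on days 2-35 (34 values), the single draw sees 7-8/34 (21-24%) of 8-day, 13-14/34 (38-41%) of 14-day and 20-21/34 (59-62%) of 21-day episodes.

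**3. Which missed episodes matter.** An unseen asymptomatic grade 3 episode of seven days or less is exempt, so missing it does no harm. The loss is confined to asymptomatic episodes that last more than seven days, or reach grade 4, and resolve before the draw.

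**4. What the draws say about duration.** A value first seen at cycle 2 day 1 has an unknown onset, and the next scheduled lipase is cycle 3 day 1, about four weeks later. If that value is not repeated and is counted, 6-7/27 (22-26%) of exempt 7-day episodes would be counted as DLTs.

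Weekly draws help but do not fix exact duration. As an illustration only, call an episode longer than seven days if it is still grade 3 exactly seven days after the first value that shows it. On that reading:

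- 14-day episodes: 6-7/27 (22-26%) are classified as longer now, against 25-27/27 (93-100%) with added draws.
- 8-day episodes: 0-1/27 (0-4%) now, against 3-4/27 (11-15%) with added draws.

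**The case against.** **Both sections can be followed as written.** Section 6.7.2 does not promise a scheduled test for every possible toxicity. Urine protein, LVEF and TSH/T4 also have no on-treatment test in cycle 1. This stands, so it would be too strong to infer that the documents contradict each other or that the DLT rule is unworkable. Lipase differs from those three in having a named exception with a duration limit.

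**Unscheduled repeats are already assumed elsewhere.** The electrolyte exception depends on correction within 48 hours, which weekly chemistry cannot show. This also stands. The point about duration is one of degree; the lack of any lipase value before the end of cycle 1 is specific.

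**The direction of bias is not settled.** A reader might infer that the schedule biases escalation towards too high an MTD. Missed events can only lower the count, but an unrepeated late value can raise it by counting an exempt episode. The documents do not show which effect is larger.

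**The durations are assumed.** No document supports durations of 8 to 14 days or uniform onset. Longer episodes are mostly seen already: 74-78% at 21 days and 93-100% (25-27/27) at 28 days.

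**Section 8.5 might seem to lose the dates.** It says "In most cases, it is acceptable to record in OnCore only the highest grade of a toxicity occurring during a particular study segment" when grades fluctuate. The same section requires DLTs to be recorded, and Section 16.2 has them reported within one business day and eCRF data traceable to source. Nothing shows that DLT decisions rest on the shortened entry, so this adds little.

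**Safeguards exist.** Symptoms can prompt a test at the weekly visits. Table 5 leaves out of its rules for other AR-42 toxicities "other lab abnormalities that are asymptomatic and/or not clinically significant per investigator", so few dose changes hang on these values. Section 6.7.4 adds that "A RP2D below the MTD may be considered given the overall tolerability of the treatment regimen". These narrow the consequence but do not restore an uncounted DLT.

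**Conclusion.** The concern holds as a gap in ascertainment. The DLT definition depends on a laboratory finding and its duration in cycle 1, and the calendar first measures that finding on days 26-29 (about days 33-36 in a 35-day cycle). Under the uniform-onset assumption, the present draw misses 70-74% of 8-day, 48-52% of 14-day and 22-26% of 21-day episodes, all of which are DLTs by the text if attributed. Three added draws would cut each of these to 0-7%.

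The net effect on the DLT count is undetermined. The effect on the MTD cannot be sized: lipase does not appear in the pazopanib laboratory tables (Tables 15 and 18), and the AR-42 pharmaceutical section is not shown in the available text. It is probably modest. A day 29 draw also falls on cycle 2 day 1, after the DLT period. It can still reveal an elevation that began in cycle 1, and the plan does not say how such a value is to be used. The reading of the schedule is secure; the size of the consequence is not.

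**What to change.** Reconcile Section 6.7.2 with Tables 19 and 20:

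- Add lipase to the blood already drawn on cycle 1 days 8, 15 and 22, and on day 29 if the cycle is extended.
- Have the sponsor state how the existing seven-day limit is to be judged from those draws. This should cover when a grade 3 value is repeated and whether a cycle 2 day 1 value bears on cycle 1 DLT. No new DLT criterion is proposed here; that choice is the sponsor's.

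The cost is one more assay on three or four existing draws and some repeat draws. A few more asymptomatic laboratory DLTs may be found.

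The main risk is false DLTs. More exempt episodes would be seen: 93-100% of 7-day ones, against 22-26% now. As an illustration, suppose a grade 3 value counted unless a repeat within seven days showed resolution, visits drifted within their 24-hour windows, and no extra repeats were done. In the worst combination of visit days, 20/27 (74%) of exempt 7-day episodes would then be counted as DLTs, against 6-7/27 now. The repeat-testing statement should therefore accompany the added draws.
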